Ha: The ophthalmic solution PRO-157 is so safe and effective in some of its different posologies when demonstrating non-inferiority when compared against Moxifloxacin and Gatifloxacin in the treatment of conjunctivitis	

Sponsor's name: Laboratorios Sophia, S.A. of C.V.

Finished Product Name: NA

Active Ingredient Name: Pazufloxacin

Methodology

Multicentric double randomized study masked.

Number of participants: 300 eyes, 60 eyes per treatment group

Diagnosis and main criteria for inclusion

Patients with bacterial conjunctivitis (signs and / or symptoms and / or culture)

Subjects aged 0 years to 99 years.

Study medication:

Pazufloxacin

- **Treatment duration:**
- - **Recruitment period: 4 months**
- - **Period of treatment: 7 days**
- - **Period of follow-up: 15 days**

Criteria for evaluation:

Efficacy measurements:

Main efficacy criterion

It will be determined as effective if there is a reduction in the number or species of bacterial flora comparing the basal culture against the final between the five different groups of patients and / or if there is a reduction or absence of the infection with the clinical evaluation through signs and symptoms such as: burning, tearing, foreign body sensation, pruritus,

photophobia, conjunctival hyperemia, chemosis, secretion, palpebral edema, membranes and / or pseudomembranes, palpebral scales and epitheliopathy

Security measurements:

Visual ability

Adverse events

INDICE

1. Summary of the study	2
2. Glossary and definitions	6
3. Administrative structure of the study	7
3.1 Parties not sponsored.	7
3.2 Sponsored parties	8
4. Background information	8
4.1 Justification	9
4.2 Non-clinical pharmacology	11
5. Clinical Studies	17
6. Hypothesis and Objectives	17
6.1 Work hypothesis	17
6.2 Objectives.	19
7. Point or points limit	19
8. Study plan	25
9. Measures to minimize deviations	29
10. Products administered	30
11. Description of the packaging	31
12. Management of the study medication	31
13. Closure of the center	33
13.1 Premature discontinuation of study	31
13.2 Center closure	31
14. Source data	33
15. Selection and withdrawal of subject of study	33
15.1 Inclusion criteria	33
15.2 Exclusion criteria	34
15.3 Criteria for patient withdrawal	36
16. Treatment of the study subjects	37
16.1 Managed treatments	37
16.2 Delivery of treatment	37
16.3 Previous and concomitant treatments	37
16.4 Treatments authorized during the study	39
16.5 Drug compliance	39
17. Methods and times of measurements	39

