7 STUDY DESIGN

7.1 Point or limit points

Criteria for the evaluation.

Efficacy measurements:

Main efficacy criterion

Efficacy will be determined by taking cultures of the lower conjunctival cul-de-sac background quantifying (colony-forming units) and identifying genus and basal and final microbial species.

It will be determined as effective if there is a reduction in the number or species of bacterial flora comparing the basal culture against the end between the five different groups of patients and / or if there is a reduction or absence of the following specific signs and symptoms: burning, tearing, Foreign body sensation, pruritus, photophobia, conjunctival hyperemia, chemosis, palpebral edema and secretion, membranes and / or pseudomembranes when comparing the study medication versus Moxifloxacin and versus Gatifloxacin from baseline to final visit.

Efficiency parameters

- The effectiveness of the drug will be evaluated by means of:

1. Clinical referral

2. Microbiological remission

Clinical remission will be evaluated by means of the signs and symptoms that the patient presents at the beginning and at the end of the study.

Variable	Operationalization	Measurement scale	Value
Secretion	Dependent Qualitative ordinal	Absent Present	Must be recorded as absent in 95% of the subjects evaluated
Conjunctival hyperemia	Dependent Qualitative ordinal	Absent Mild Moderate Severe	You must comply with the following: • Absent \geq 95.0% • Mild \leq 5.0% • Moderate \leq 2.5% Severe \leq 1.0%
Chemosis	Dependent Qualitative ordinal	Absent Present	Must be recorded as absent in 95% of the subjects evaluated
Eyelid edema	Dependent Qualitative ordinal	Absent Present	Must be recorded as absent in 95% of the subjects evaluated
Corneal epithelial defects	Dependent Qualitative ordinal	Affected area, percentage	Percentage of affected area less than 95%

The microbiological remission will be evaluated by means of the culture taken from the conjunctival sac fundus.

Variable	Operationalization	Measurement scale	Value
Culture	Dependent Discrete quantitative	UFC * / ml Eradication Reduction Proliferation	Must be recorded as absent in 95% of the subjects evaluated

* Colony forming units

The drugs under study will be considered effective if the patient has any of the following:

1. Clinical remission + Microbiological remission.
2. Clinical referral.
3. Microbiological remission.

Security measurements:

Adverse events and visual capacity.

Evaluation parameters

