• The safety of the use of PRO-157 will be evaluated in the visits indicated in the schedule, through the following parameters:

1. Visual capacity
2. Eye surface
3. Exploration of the previous segment
4. Exploration of the posterior segment
5. Burning
6. Foreign body sensation
7. Lachrymation
8. Conjunctival hyperemia
9. Itching
10. Photophobia
11. Chemosis
12. Tear discharge
13. Eyelid edema
14. Membranes / pseudomembranes
15. Scales
16. Corneal epithelial defects
17. Adverse events

It will be considered that the drug under evaluation is safe for use in humans if there are no changes in the parameters indicated in more than 5% of the subjects, in both eyes, if the

patient goes to all the visits of the study and complies with adherence to treatment $\geq 80\%$ during the time of evaluation of the study.

Variable	Operationalization	Measurement scale	Value
Visual ability	Independent Discrete quantitative	Points logMAR 0-1 0 = Snellen 20/20	Do not present change in 1 line in the Snellen letter or in 1 logarithmic point (log MAR)
Ocular surface	Dependent Qualitative ordinal	Absent Present	Abnormalities in any area of the ocular Surface
Exploration of the previous segment	Dependent Qualitative ordinal	Normal Abnormal	Abnormalities in any of the structures included: cornea, iris, pupil, irido-corneal and crystalline angle.
Exploration of the posterior segment	Dependent Qualitative ordinal	Normal Abnormal	Abnormalities in any of the structures included: vitreous, retina, macula and the optic nerve
burning	Dependent Qualitative ordinal	Absent Present	Must be recorded as absent in 95% of the subjects evaluated
strange body sensation	Dependent Qualitative ordinal	Absent Present	Must be recorded as absent in 95% of the subjects evaluated
tearing	Dependent Qualitative ordinal	Absent Present	Must be recorded as absent in 95% of the subjects evaluated

Secretion	Dependent Qualitative ordinal	Absent Present	Must be recorded as absent in 95% of the subjects evaluated
Conjunctival hyperemia	Dependent Qualitative ordinal	Absent Mild Moderate Severe	You must comply with the following: Absent ≥ 95.0% Mild ≤ 5.0% Moderate ≤ 2.5% Severe ≤ 1.0%
Photophobia	Dependent Qualitative ordinal	Absent Mild Moderate Severe	You must comply with the following: Absent ≥ 95.0% Mild ≤ 5.0% Moderate ≤ 2.5% Severe ≤ 1.0%
Chemosis	Dependent Qualitative ordinal	Absent Present	Must be recorded as absent in 95% of the subjects evaluated

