8 STUDY PLAN

This is a phase II, randomized, double masked, multicentre, national study.

This study will be carried out with 60 eyes with diagnosis of bacterial conjunctivitis, by treatment group, of patients of the ophthalmological consultation.

Patients diagnosed with bacterial conjunctivitis (signs and / or symptoms and / or culture) recruited will be treated for 7 days with any of the three posologies of PRO157, Moxifloxacin, or Gatifloxacin. The randomization of any of the medications will be coordinated by a member of the research team previously designated who will not be masked and will be responsible for indicating to the patients how to apply the drops, emphasizing the patients of by no means mentioning the evaluating physician with the frequency who applies the study medication.

No patient may use the aforementioned treatment more than the prescribed time. For purposes of the protocol, the infected eye (s) will be taken into account at baseline but the study medication and procedures will be applied and will always be done in both eyes to protect the healthy eye and the possibility of infection if Do not be infected from the beginning.

The study is divided into the following periods:

There will be a total of 3 visits which are divided into 1 baseline visit (day 1) 1 treatment visits (day 3), 1 final visit (day 8). A telephone call will finally be made to evaluate adverse events after 15 days of the last application of medication (day 23)

At each visit from the baseline a clinical photograph of the eyes will be made, each of them must be identified by patient and visit number and delivered once the 30 patients are completed on a CD or USB.

1. Period of treatment of 7 days (from day 1 to 7) where any of the following posologies are applied according to randomization:

PRO157 1 drop 2 times a day in both eyes.
PRO157 1 drop 3 times a day in both eyes.
PRO157 1 drop 4 times a day in both eyes.
Moxifloxacin 1 drop 3 times a day in both eyes
Gatifloxacin1 drop 3 times a day in both eyes

The study medications will be delivered by a coordinator (not blinded) or a person previously designated by the principal investigator, who will indicate how to apply the study medication according to the randomization and will place special emphasis on not mentioning the principal investigator or designee. perform the evaluations as the drop or any characteristic of the jars is applied.

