$Z_{1-\alpha/2} = Z_{0.975}$ de la distribución normal estandarizada que deja un area de 0.975 a la izquierda. Implica una confiabilidad del 95% 1.960

β = Probabilidad de error tipo 2 0.200

$1-\beta$ = Percentil unilateral para la beta asignada 0.800

$Z_{1-\beta} = Z_{0.80}$ de la distribución normal estandarizada que deja un area de 0.80 a la izquierda. Implica un poder del 80% 0.842

m' = Tamaño de muestra

$$m' = \frac{(z_{1-\alpha/2} \sqrt{(r + 1) * P * Q} + z_{1-\beta} \sqrt{r * P1 * Q1 + P2 * Q2})^2}{r * (P2 - P1)^2}$$

$$m' = \frac{(1.960 \sqrt{(1.00+1) 0.79 * 0.21} + 0.842 \sqrt{1.00 * 0.92 * 0.08 + 0.66 * 0.34})^2}{1.00 (0.66 - 0.92)^2}$$

$$m' = 36.373$$

m = Tamaño de muestra corregido

$$m = 0.25 m' * \left[1 + \sqrt{1 + \frac{2(r + 1)}{m' * r * |P2 - P1|}} \right]^2$$

$$m = 44 \quad \begin{array}{l} \text{Tamaño de muestra para el grupo de referencia (Controles): } m_1 = r * m \\ \text{Tamaño de muestra para el grupo de estudio (Casos): } m_2 = m \end{array} \quad \begin{array}{l} 44 \\ 44 \end{array}$$

Analyzed data set

The data will be analyzed in two groups, one will be made up of the population evaluable by Intention to Treat (ITT) in which each of the variables is described, the ITT population will be constituted by all the recruited subjects who have received at least one dose of study treatment.

Others will be the evaluable population Per Protocol (PP) which is the subset of ITT composed of all subjects without any major deviation from the protocol, in which the bivariate analysis will be performed.

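### Section 7.1 sets clinical-remission marks on raw observed percentages with no allowance for sampling error: at 60 independent eyes, an arm truly at 95% misses a single sign's mark 35% of the time, and the 1.0% severe-hyperemia mark is a zero-event rule

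*Combined protocol and SAP*

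**What the plan says.** Section 7.1 assesses efficacy through clinical and microbiological remission. In the clinical-remission table, secretion, chemosis and eyelid edema each have the value "Must be recorded as absent in 95% of the subjects evaluated". The hyperemia row opens with "You must comply with the following" and lists limits for absent, mild, moderate and severe. The safety table in the same section repeats those limits: "Absent ≥ 95.0% Mild ≤ 5.0% Moderate ≤ 2.5% Severe ≤ 1.0" percent. The culture row of the microbiological table uses the same 95% wording as the binary signs.

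The section then says: "The drugs under study will be considered effective if the patient has any of the following". The list is both remissions, clinical remission alone, or microbiological remission alone.

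The summary gives the size as "300 eyes, 60 eyes per treatment group", and section 8 also gives 60 eyes per group. Section 23 contains a drug-versus-placebo sample size, the two analysis sets, and a per-protocol set "in which the bivariate analysis will be performed", with no method named. No interval, test, tolerance or probability of a wrong result is attached to the marks in either section.

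**The concern.** A percentage observed in a small arm is treated as if it were the true rate. The marks are worded as requirements, and clinical remission alone is one of the listed routes to calling a drug effective. An arm can therefore miss a mark although its true rate meets it, or meet the mark although its true rate falls short.

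The stated hypothesis (section 6.1) is non-inferiority to moxifloxacin and gatifloxacin, and the main criterion in section 7.1 is also comparative. A cut-off applied to one arm at a time cannot answer that question. Arms with the same true rate can land on opposite sides of it, and with three PRO-157 posologies such chance results could also colour the choice between them.

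This would remain even if every scale and denominator in the table were settled.

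**Working it through.** **The plan's own figures.** The documents give no operating characteristic for the marks, so there is none to reproduce. The sample-size annex can be checked, to see whether 60 per arm came from the marks. The corrected Fleiss formula is m = 0.25 m′ [1 + √(1 + 4/(m′ |P2 − P1|))]².
- Absolute efficacy: m′ = 135.272 and difference 0.165 give m = 147.1 (stated 147).
- Specific efficacy: m′ = 36.373 and difference 0.2622 give m = 43.7 (stated 44).

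Both agree. Both concern bacterial eradication on drug versus placebo, so the 60 eyes were not derived from the clinical marks.

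**Inputs.** Marks from section 7.1; 60 eyes per arm from the summary and section 8. Assumptions: percentages are per arm, eyes are independent, and the 95% mark means at least 95%, as the hyperemia row states.

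**Marks as counts at n = 60.**
- Absent at least 95%: 0.95 × 60 = 57, so at most 3 eyes with the sign.
- Moderate at most 2.5%: 1/60 = 1.67% passes and 2/60 = 3.33% fails, so at most 1.
- Severe at most 1.0%: 1/60 = 1.67% already fails, so 0.

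**One binary sign.** With true absence rate p, P(pass) = P(X ≤ 3), X ~ Binomial(60, 1 − p). At p = 0.95 the terms for 0, 1, 2 and 3 eyes are 0.046 + 0.145 + 0.226 + 0.230 = 0.647, so P(fail) = 0.353.

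| True absence | Fails one sign | Passes one sign |
|---|---|---|
| 90% | 86.3% | 13.7% |
| 92% | 71.7% | 28.3% |
| 95% | 35.3% | 64.7% |
| 97% | 10.6% | 89.4% |
| 98% | 3.2% | 96.8% |

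**Hyperemia limits, taken singly.**
- True severe rate 1.0%: P(fail) = 1 − 0.99^60 = 45.3%.
- True moderate rate 2.5%: P(at least 2 of 60) = 44.4%.

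**Opposite results in two independent arms with the same true rate.** 2 × P(pass) × P(fail):
- 95%: 2 × 0.647 × 0.353 = 46%.
- 97%: 2 × 0.894 × 0.106 = 19%.
- 98%: 2 × 0.968 × 0.032 = 6%.

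**What a bare pass shows.** An observed 57/60 has an exact 95% confidence interval of 86.1% to 99.0%.

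**Sensitivity to the unit and the number evaluated (true absence 95%).**
- 59 evaluated: at most 2 may have the sign; fails 57.1%.
- 30 subjects, if all contribute both eyes: at most 1 with the sign, 0 moderate, 0 severe; fails one sign 44.6%.
- 60 eyes with the mark read strictly as above 95%: at most 2; fails 58.3%.

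**The case against.** Several objections have force.

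- **The 35% is a boundary value.** Any cut-off misclassifies often when the truth sits on it. At 97% or 98% the failure rate is much lower, and the documents give no expected rates for the clinical signs: the published figures in section 23 are for bacterial eradication. This stands, so 35% should be read with the table. The error also runs the other way, as the 28% pass rate at 92% shows.
- **The clinical marks are not decisive alone.** Microbiological remission by itself also counts as effective, and that rule is phrased per patient. This stands. The culture row, however, carries the same 95% wording, so that route has the same weakness.
- **The unit is unclear.** The mark is written for subjects while the sample is counted in eyes, and section 8 allows one or both eyes to be infected. An arm could hold 30 to 60 subjects. The size of the error moves with that number, but the problem does not go away.
- **A comparison is stated elsewhere.** Sections 6.1 and 7.1 do aim at the two comparators. That is the stated aim, but the marks do not serve it and section 23 names no method that would.
- **Fixed go/no-go marks can be legitimate in phase II.** They can, when the chance of passing at the relevant true rates is given. Here it is not.

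A reader might go further and infer that all signs must pass together, and multiply the single-sign probabilities. The documents do not support this: section 7.1 does not say how the signs combine, and signs of the same inflammation are unlikely to be independent.

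**Conclusion.** The concern holds for the marks taken one at a time. Read per arm with 60 independent eyes, the section 7.1 marks are count rules with no allowance for sampling error. The result on one sign is unreliable when the true rate is near 95% and fairly reliable once it reaches about 98%. The severe-hyperemia mark allows no events at all, although it is written as 1.0%.

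These sizes rest on the per-arm reading, independent eyes, complete evaluation of 60, and 95% taken as at least 95%. Other units or counts change the percentages but leave the problem in place.

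A reader might also infer that the overall verdict on each arm is mostly chance. The documents do not support that: the true sign rates are unknown, the combination rule is unstated, and a second route to effectiveness exists. The narrower point is enough to justify a change, because these cut-offs cannot answer the non-inferiority question.

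**What to change.** In section 7.1, and wherever the same marks recur in its safety table:

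1. Keep the 95, 5, 2.5 and 1.0 percentages as descriptive targets only.
2. State the unit, subject or eye. Report each sign per arm as the percentage absent with an exact 95% confidence interval if each patient counts once, or an interval that allows for clustering if both eyes of a patient count.
3. Base the clinical-efficacy conclusion on the difference in clinical remission between each PRO-157 arm and each comparator, with its 95% confidence interval, and carry this into section 23. This needs a definition of clinical remission for a single patient or eye and a non-inferiority margin. The documents give neither, and the sponsor must supply and justify both.
4. If any mark is kept as a decision rule, state the count it implies at the actual arm size and its probability of passing at the target rate and at rates on either side.

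The cost is wording; the change itself calls for no new assessments. The simple pass/fail statement per arm is lost. The interval for a difference will also be wide: at 60 independent eyes per arm and 95% remission its half-width is 1.96 × √(2 × 0.95 × 0.05/60) = 0.078, about 8 points. Whether that is precise enough depends on the margin chosen.

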Eyelid edema	Dependent Qualitative ordinal	Absent Present	Must be recorded as absent in 95% of the subjects evaluated
Membranas Pseudomembranes	Dependent Qualitative ordinal	Absent Present	Must be recorded as absent in 95% of the subjects evaluated
Scales	Dependent Qualitative ordinal	Absent Present	Must be recorded as absent in 95% of the subjects evaluated

Epithelial defects corneal	Dependent Qualitative ordinal	Affected area, percentage	Percentage of the affected area 95%
Adverse events	Dependent Qualitative ordinal	serious Not Serious	Must be recorded as absent in 95% of the subjects evaluated

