 - Finally, through the pinhole, the same procedure will be carried out.

Normal values: visual acuity or visual capacity will be expressed in decimals, where 0.0 will be the maximum normal score. In the case of people who do not know how to read, the test will be done with special cards of figures or numbers and the VA will be defined with the same LogMar scale, for patients of very early ages such as RN, infants or uncooperative preschoolers. AV as it perceives and follows light or does not perceive or follow light.

In offices where LogMar is not available, you can measure the VA with the card you normally use and convert it to the LogMar scale for which the following table of equivalences helps.

Equivalence between the different AV scales

MAR (min arc)	Log MAR	Snellen (d=6m)	Snellen (d=20 ft)	Escala decimal	Keeler A
100	2.0	6/600	20/200	0.01	
79	1.9	6/480	20/1600	0.0125	20*
63	1.8	6/380	20/1250	0.016	19*
50	1.7	6/300	20/1000	0.02	18*
40	1.6	6/240	20/800	0.025	17*
32	1.5	6/190	20/630	0.032	16*
25	1.4	6/150	20/500	0.04	15*
20	1.3	6/120	20/400	0.05	14*
15.8	1.2	6/95	20/320	0.063	13*
12.5	1.1	6/75	20/250	0.08	12
10.0	1.0	6/60	20/200	0.1	11
8.0	0.9	6/48	20/160	0.125	10
6.3	0.8	6/38	20/125	0.16	9
5.0	0.7	6/30	20/100	0.2	8
4.0	0.6	6/24	20/80	0.25	7
3.2	0.5	6/19	20/63	0.32	6
2.5	0.4	6/15	20/50	0.4	5
2.0	0.3	6/12	20/40	0.5	4
1.58	0.2	6/9.5	20/32	0.63	3
1.25	0.1	6/7.5	20/25	0.8	2
1.0	0.0	6/6	20/20	1.0	1
0.8	-0.1	6/4.8	20/16	1.25	
0.63	-0.2	6/3.8	20/12.5	1.6	
0.5	-0.3	6/3	20/10	2.0	

Biomicroscopy Previous

It refers to the revision of the entire anterior segment: cornea, iris, pupil, anterior chamber, crystalline and / or (IOL).

It will be qualified as follows:

Normal.

Abnormal.

Abnormality that does not affect the result of the study.

If any of the structures has any special description that you write down in comments of that same section in the FRC.

Conjunctival hyperemia

Which is defined as the simplest reaction of the conjunctiva to a stimulus, we see a red appearance secondary to the vasodilation of the conjunctival vessels of variable intensity. It will be classified according to the analogous visual scale of hyperemia. VII

1.- Very Mild

2. Mild

3.- Moderate

4.- Severe

Foreign body sensation

Burning

Lachrymation

Eyelid scales

Eyelid edema

Membranes and / or pseudomembranes

Epitheliopathy

These symptoms will be described as present or absent,

Secretion will also have to be described

Fluorescein and green lysamin stain

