Fluorescein staining will be performed, standardization of this scan is done as follows:

1. With the patient in front of the lamp prior instillation of topical anesthesia Ponti Ofteno that will be provided by Laboratorios Sophia, S.A. of C.V.
- 2.- The lower eyelid of the patient will be gently grabbed, first on the right side and then on the left side, asking the patient to turn upwards so that with this maneuver a greater area of the lower bulbar conjunctiva is exposed, then the filter paper will be placed moistened with a drop of anesthetic and the surface of the eye will be touched with it for a second in the aforementioned area, subsequently the patient will be asked to blink several times and proceed to examine it without specifying corneal region, the same procedure will be performed for the analysis of the conjunctiva with lysamine green:

Absent (without staining)

Medium (less than 10% of the surface with staining)

Moderate (from 10 to 50% with surface staining)

Severe (more than 50% of the surface)

Membranes and pseudomembranes

They are formed by exudates adhering to the inflamed conjunctival epithelium, the difference between one and another is that the latter are removable.

Your presence or absence will be reported.

Subsequent Segment Review

It refers to the revision of the entire posterior segment, particularly: vitreous, retina, macula and optic nerve. It will be qualified as follows:

Normal.

Abnormal.

Abnormality that does not affect the result of the study.

If any of the structures has any special description that you write down in comments of that same section in the FRC.

Sampling for central laboratory:

(This is a general procedure, it does not mean that it should be done as such, that procedure will be punctually described by the central laboratory where the crops will be sent).

- 1.- After cleaning hands and putting on latex gloves.
- 2.- Take the swab contained in the package of the means of transport with the index fingers and thumb of the right hand while with the index finger of the left hand the lower eyelid is gently pulled exposing the bottom of the bag and thus be able to take the sample of it
- 3.- By touching the palpebral conjunctiva the applicator is rotated to take as much sample as possible.
- 4.- Place the swab in the transport medium.

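### Two of the five clinical-remission items, hyperemia and corneal epithelial defects, do not match the scales section 17 gives for measuring them, and the corneal limit of under 95% affected area screens out almost nothing

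*Combined protocol and SAP*

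**What the plan says.** Section 7.1 (Efficiency parameters) judges clinical remission on five signs: secretion, conjunctival hyperemia, chemosis, eyelid edema and corneal epithelial defects. It then lists three routes by which a drug counts as effective, and clinical remission on its own is one of them.

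- **Hyperemia, section 7.1.** The scale is "Absent Mild Moderate Severe". The limits, the same in the efficacy and safety tables, are "Absent ≥ 95.0% Mild ≤ 5.0% Moderate ≤ 2.5% Severe ≤ 1.0" per cent.
- **Hyperemia, section 17 (Methods and times of measurements).** "It will be classified according to the analogous visual scale of hyperemia", followed by four grades: 1 Very Mild, 2 Mild, 3 Moderate, 4 Severe.
- **Corneal epithelial defects, section 7.1.** The efficacy value is "Percentage of affected area less than 95" per cent. The safety table has "Percentage of the affected area 95" per cent, without saying whether the area must be above or below it.
- **Nearest measurements in section 17.** Epitheliopathy is in a list of findings of which the plan says "These symptoms will be described as present or absent". Fluorescein and lissamine green staining is graded in four bands, from "Absent (without staining") through under 10% and 10 to 50%, up to "Severe (more than 50% of the surface").

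For secretion, chemosis and eyelid edema, the value is absence in 95% of the subjects evaluated.

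**The concern.** An endpoint table and the instructions for filling it in should use the same categories. Here they do not, for two items out of five.

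For hyperemia, an evaluator who follows section 17 literally has no grade for a clear eye, and may record Very Mild, a grade the remission table does not contain. Someone must later decide whether Very Mild means absent or mild. If that choice is made after the data are in, or differs between sites in a multicentre trial, the remission rate moves for reasons unrelated to treatment.

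For the cornea, a limit that fails only eyes with 95% or more of the area affected will hardly separate recovered from unrecovered eyes, or one arm from another. The working hypothesis is non-inferiority to moxifloxacin and gatifloxacin, and an item that nearly every eye passes makes arms look alike whatever the drugs do.

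**Working it through.** The plan has no figure to reproduce on this point. The check sets the tables side by side and then applies the limits to the planned group size.

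| Item | Section 7.1 | Section 17 | Conflict |
|---|---|---|---|
| Hyperemia | Absent / Mild / Moderate / Severe | Very Mild / Mild / Moderate / Severe | No absent grade in section 17; no Very Mild in 7.1; no mapping |
| Corneal defects | Percentage of area, limit 95% | Epitheliopathy present/absent; staining in bands cut at 10% and 50% | Neither record shows on which side of 95% an eye lies |

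**Hyperemia.** Inputs: the section 7.1 limits and 60 eyes per group (sections 1 and 8). I assume the limits apply to eyes; the table does not give the denominator.

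- Absent: 0.95 × 60 = 57, so at least 57 eyes.
- Mild: 0.05 × 60 = 3, so at most 3.
- Moderate: 0.025 × 60 = 1.5, so at most 1.
- Severe: 0.01 × 60 = 0.6, so none.

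The first failing count of Absent is 56, which leaves 60 − 56 = 4 eyes. Suppose those four are recorded as Very Mild and the other 56 are clear and recorded as absent:

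- Very Mild counted as Absent: 60/60 = 100% Absent. The limit is met.
- Very Mild counted as Mild: 56/60 = 93.3% Absent and 4/60 = 6.7% Mild. Both limits are missed.

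The same eyes pass or fail on a coding choice that the plan does not make.

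**Corneal defects.** Applying the efficacy value directly, areas of 0, 9, 50, 51, 75 and 94% all pass; only 95% or more fails. This needs no link to any other scale.

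If the staining bands were taken as the measure, which the plan does not state, every Absent, Medium and Moderate eye would pass. So would the part of the Severe band between 50% and 95%: (95 − 50)/(100 − 50) = 45/50, or 90% of the band's width. A recorded grade of Severe would not show on which side of 95% the eye lay.

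If epitheliopathy is taken as the measure, there is no percentage to compare with the limit at all.

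**The case against.** The strongest reply concerns hyperemia. A reader might infer that no site can record Absent, so that the 95% target fails in every arm by construction. The documents do not support that. Section 7.1 itself includes Absent, and section 17 can be read as grading only the redness that is present, with a clear eye simply recorded as absent. Section 17 also cites an outside scale and promises evaluators detailed rating rules; neither these nor the case report form are in the documents. What stands is the absence of a mapping and the unplaced Very Mild grade.

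A reader might also infer that the plan deliberately counts eyes with severe staining as remitted. That goes too far as well. No section ties the staining bands to corneal epithelial defects; the schedule lists staining and epitheliopathy separately, and staining is read without specifying a corneal region. The 95% may be a slip or a translation error. But the documents do not reveal the intended limit, so an analyst cannot safely supply one, and the stated limit passes near-total involvement with or without the staining link.

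Three further points limit the reach. The main efficacy criterion accepts a reduction in signs as well as their absence, and its list of signs in section 7.1 omits corneal defects (the section 1 summary includes epitheliopathy). Microbiological remission is a separate route to effectiveness and is untouched. And the plan does not say how the five items combine, so the effect of either item on the overall remission rate cannot be computed. All three stand, but none repairs the two items.

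**Conclusion.** The point holds as an inconsistency and a faulty threshold, and both are wrong as written. Two of the five items are affected, in a component that suffices alone for a finding of effectiveness.

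- The hyperemia result depends on an unplanned recoding. With 60 eyes per group, four Very Mild eyes can be enough to turn a pass into a fail.
- The corneal value is met by any area below 95%, conflicts with its undirected counterpart in the safety table, and cannot be scored from the grades section 17 asks for.

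The four-eye figure assumes that the limits apply to 60 eyes and that the remaining 56 are recorded as absent. The statement about the staining bands is conditional on a link that the plan does not make. No claim is made that hyperemia fails in all arms or that the Absent rate must be zero.

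**What to change.** 1. Use one hyperemia scale, with an explicit absent grade, in both section 7.1 tables and in section 17. State before unmasking which grades count as remission and where Very Mild falls.
2. Restate the corneal value on something the trial already records, for example epitheliopathy absent, in line with the other signs, or a named staining grade. The sponsor should confirm the intended limit. Align the efficacy and safety tables.
3. State the remission rule per patient or per eye, including how the five items combine. Section 7.1 applies remission to the patient, but most of its values are percentages of a group, so correcting the two scales alone would still leave individual remission undefined.

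The cost is wording in the protocol and possibly the case report form, with no new assessment. The corneal item may become harder to meet; the documents give no rate from which to say by how much.
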